At Study Visit 1, participants randomized to the SOC will complete the baseline questionnaire to collect sociodemographic, HIV clinical and treatment history, self-reported ART medication adherence [28], quality of life [29-31], and resource allocation data. Study staff will review participant records to collect data on clinic initiation start date, opportunistic infection history, ART initiation date, ART regimen history, CD4 count and viral load result histories. A single 10cc blood specimen will be drawn for storage for future testing for viral load, resistance testing, and drug therapeutic monitoring (See Table 3 – Page 18). A voided urine specimen will also be collected for future testing for therapeutic drug monitoring. Participants will be referred to clinic counselors who will conduct adherence support counseling as per standard clinical procedures. A follow-up study visit will be scheduled 2-3 months from the baseline date (depending on the local clinic policy), with the exception of pregnant women, who will be asked to return in approximately 1 month. Any interim clinical visits that are indicated by the clinic staff will be maintained. The participant will be instructed to continue their current ART regimen until at least the next clinical visit.

B. Visit 2A-SOC: Repeat Viral Load Testing Visit

At Study Visit 2A, participants in the SOC arm will undergo blood collection for viral load testing in keeping with WHO guidelines. An additional tube 10cc tube will be drawn for storage for future testing for viral load, resistance testing, and drug therapeutic monitoring. A voided urine specimen will also be collected for future testing for therapeutic drug monitoring. A study questionnaire will be administered to assess self-reported ART medication adherence. No other procedures are scheduled at this visit. Participants will be notified that study staff will contact them as soon as their results are available, to request return to clinic for further management. The participant will be instructed to continue their current ART regimen until at least the next clinical visit. As soon as the viral load result is available, study participants will be contacted by phone and requested to return to clinic for review. If the viral load is indeterminate or not completed for any reason, study staff will request that the participant return for a repeat viral load test.

Table 2. Summary of study procedures

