Study Arm	Visit	Blood Collection	Study Forms	Other Procedures/Forms
Standard of Care Arm	Visit 1-SOC	10 cc EDTA	-Baseline questionnaire -Tracking form -Adherence questionnaire -Quality of life (EQ5D) -Resource use questionnaire -Staff resource use -ART and laboratory history	-Adherence counseling -Collection of a voided urine specimen
	Visit 2A-SOC	4 cc EDTA + 10 cc EDTA	-Staff resource use -Adherence questionnaire	-Viral load test -Collection of a voided urine specimen
	Visit 2B-SOC	None	-Staff resource use	-Review viral load results -Adherence counseling
	Visit 3	4cc EDTA + 10cc EDTA	-Adherence questionnaire -Quality of life (EQ5D) -Resource use follow-up -Staff resource use -Interim ART and laboratory history	-Viral load test, with reflex resistance testing if detectable -Collection of a voided urine specimen
Resistance Testing Arm	Visit 1-RT	4cc EDTA + 10cc EDTA	-Baseline questionnaire -Tracking form -Adherence questionnaire -Quality of life (EQ5D) -Resource use questionnaire -Staff resource use -ART and laboratory history	-Adherence counseling -Resistance test -Collection of a voided urine specimen
	Visit 2-RT	None	-Staff resource use	-Review resistance test results -Adherence counseling
	Visit 3	4cc EDTA + 10cc EDTA	-Adherence questionnaire -Quality of life (EQ5D) -Resource use follow-up -Staff resource use -Interim ART and laboratory history	-Viral load test, with reflex resistance testing if detectable -Collection of a voided urine specimen

C. Visit 2B-SOC: Viral Load Testing Results and Therapeutic Management

At Study Visit 2B, study clinicians will review the viral load result. Participants with a viral load $\leq 1,000$ copies/mL will continue their first-line (NNRTI-based) ART regimen without change. Participants with a viral load $>1,000$ copies/mL will change ART regimen to a second-line, protease inhibitor (PI)-based or, if available, integrase inhibitor (II)-based therapy. Clinicians will also be encouraged to change the nucleos(t)ide reverse transcriptase component of the regimen (for example, changing from zidovudine to tenofovir), based on prior exposures, as well as WHO and national guidelines. All regimen decisions will be made by the study clinician, in cooperation with clinic staff at the study sites. In the case of complex

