management issues, the site principal investigators ([name] in Mbarara and [name] in Durban) will be contacted to offer input. At the conclusion of Visit 2B-SOC, participants in the SOC arm will be scheduled for a final study visit approximately 9 months after enrollment. A final visit at this time is chosen to allow ample time for drug suppression for participants with detectable viral load, and to ensure balance in observation time between study arms. Non-study clinical visits for routine clinical care and adherence counseling recommendations will continue in the interim as determined and scheduled by clinic staff.

D. Visit 3: Outcome Assessment

At Study Visit 3, participants will undergo repeat blood testing for plasma viral load and, if the viral load is detectable, reflex resistance testing will be performed. An additional 10cc tube will be drawn for storage for future testing for viral load, resistance testing, and drug therapeutic monitoring. A voided urine specimen will also be collected for future testing for therapeutic drug monitoring. A study questionnaire will be administered to assess resource allocation, ART medication adherence, and quality of life. Study staff will review participant records to update interim CD4 count, viral load, and ART regimen data. Results of viral load and resistance testing from this visit will be immediately made available to clinic staff for further patient management. At the conclusion of Visit 3, study procedures will be complete.

E. Missing and Late Appointments

If study participants do not present for study visits, study staff will call them to encourage return to clinic for continuation or completion of procedures. For participants who do not return within 7 days of a scheduled visit and unreachable by phone, a study staff member will attempt to track them at home using a standardized lost-to-follow-up form and procedures developed and used successfully both for program and clinical care in Mbarara for over 10 years [32, 33]. If participants are located, study staff will encourage them to return to clinic to complete procedures and/or conduct the blood draw and questionnaire in the field if the participant agrees.

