During the COVID-19 pandemic, participants who do not present for regularly-scheduled HIV clinic appointments will be phoned when contact information is available. Rather than tracking at home for participants that cannot be reached, tracking will be delayed until the COVID-19 pandemic subsides and regularly scheduled study procedures can resume.

VI. STUDY PROCEDURES FOR PARTICIPANTS RANDOMIZED TO RESISTANCE TESTING ARM

A. Visit 1-RT: Baseline Visit for Resistance Testing Participants

At Study Visit 1, participants randomized to the RT will complete the baseline questionnaire to collect sociodemographic, HIV clinical and treatment history, self-reported ART medication adherence, quality of life, and resource allocation data. Study staff will review participant records to collect data on clinic initiation start date, opportunistic infection history, ART initiation date, ART regimen history, CD4 count and viral load result histories. Upon completion of the baseline questionnaire, participants will undergo phlebotomy for resistance testing. Participants will be notified that study staff will contact them as soon as their results are available, to request return to clinic for further management. A voided urine specimen will also be collected for future testing for therapeutic drug monitoring. Upon completion of the study procedures, participants will be referred to clinic counselors who will conduct adherence support

counseling as per standard clinical procedures. The participant will be instructed to continue their current ART regimen until at least the next clinical visit. When the resistance test result is available, study participants will be contacted by phone and requested to return to clinic for review.

B. Visit 2-RT: Resistance Testing Results and Therapeutic Management

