Study data coordinators will perform routine reviews of data quality to identify unusual values and missing data entries. Initial analyses will include common exploratory data analyses, table construction, and scatterplots to assist in data quality control, randomization balance, and exploring for possible outliers or leverage points. For our analysis of the primary outcome, we will use a two-sample test of binomial proportions to compare the proportions of participants in each arm who achieve virologic suppression at the study conclusion. For our primary analysis we will conduct an intention to treat analysis. For this analysis, any study participant without a confirmed viral load result at the 9-month study endpoint will be considered as having a detectable viral load (failure). In secondary analyses, we will conduct as-treated analyses for any study participants who do not complete resistance testing in the RT arm or participant who do receive resistance testing in the SOC arm, as documented by clinic records. We will also conduct a sensitivity analysis by censoring participants who are lost-to-follow-up during study procedures and do not have a recorded viral load at study conclusion. The unadjusted comparison of outcome rates will be followed by adjusted comparisons via logistic regression, adjusting for other confounding factors that may explain any heterogeneity or possibly confound assigned treatment and outcome, despite treatment randomization.

The primary analyses will be followed by similar statistical analyses of secondary endpoints including the proportions suppressed on first-line therapy, rates of resistance, rates of retention in care, and the 9-month mortality rate. We will compare health related quality of life measures within participants between baseline and study conclusion using paired t-tests.

C. Economic Analyses

1. Budget Impact Analysis

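### The as-treated analysis groups by post-randomization receipt of resistance testing under unstated rules; at an assumed 5% early loss, its bias with no true effect could be 0 to about 6.5 points

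*Combined protocol and SAP*

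**What the plan says.** Section X.B.4 (Efficacy Analysis Plan) gives the as-treated analysis one sentence. For the RT arm, "we will conduct as-treated analyses for any study participants who do not complete resistance testing in the RT arm". For the SOC arm it adds "or participant who do receive resistance testing in the SOC arm, as documented by clinic records". The section does not say what completing means, whether non-completers are moved to the other group or dropped, or how a missing Visit 3 viral load is treated here.

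Two neighbouring rules bear on the last question. In the ITT analysis, "any study participant without a confirmed viral load result at the 9-month study endpoint will be considered as having a detectable viral load (failure"). Separately, "We will also conduct a sensitivity analysis by censoring participants who are lost-to-follow-up during study procedures".

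The visit schedule makes the definition matter. RT blood is drawn at Visit 1-RT. Section VI.A then says "When the resistance test result is available, study participants will be contacted by phone and requested to return to clinic for review", and Table 2 lists "Review resistance test results" under Visit 2-RT, a separate return visit. Under Section V.B, "participants in the SOC arm will undergo blood collection for viral load testing in keeping with WHO guidelines"; Table 2 schedules no such repeat test for RT between Visits 1 and 3. At Visit 3 in both arms, "if the viral load is detectable, reflex resistance testing will be performed".

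**The concern.** An as-treated comparison gives up randomization. Here the grouping variable may depend on coming back to clinic or on the assay succeeding, and either can be linked to suppression.

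Suppose completion means that the result was reviewed, and non-completers are reclassified. An RT participant lost after Visit 1 then joins the SOC group, while an SOC participant lost at the same point stays there. If missing counts as failure, early losses from both arms count against SOC and none against RT, which is the direction of the study hypothesis. A reclassified RT participant also did not receive SOC management, having had no scheduled repeat viral load.

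This is the only planned analysis of the effect of actually receiving testing, and its rules could be settled after the results are known.

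**Working it through.** **Inputs from the plan (Section X.A).** 420 per arm; 68% suppressed in SOC; two-sample test of proportions at 5% (taken as two-sided); 5% allowance for invalid tests; target difference 10 points.

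**Assumed inputs.** The plan gives no loss-to-follow-up rate and no genotype failure rate. 5% is used for scale, with a range. The plan's own 5% concerns invalid tests, not losses.

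**The plan's own figure.** With 420 × 0.95 = 399 per arm, the usual formula gives power 0.712, 0.891 and 0.973 for differences of 8, 10 and 12 points. With a continuity correction it gives 0.684, 0.875 and 0.967, against the stated 0.69, 0.88 and 0.97. The inputs are therefore read correctly.

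**Reading 1: completion = result reviewed.** Let *L* be the share of each arm lost before its second visit and never recovered, and *p* = 0.68 the suppression among those retained in both arms (no true effect).

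*Non-completers moved to SOC, missing = failure.* RT rate = *p*, with 420(1−*L*) people. SOC rate = *p*(1−*L*)/(1+*L*), with 420(1+*L*) people. Gap = 2*pL*/(1+*L*). At *L* = 0.05:
- RT: 399 people at 68.0%.
- SOC: 441 people at 0.68 × 0.95/1.05 = 61.5%.
- Gap: 2 × 0.68 × 0.05/1.05 = 6.5 points. Expected z is 1.96, so p<0.05 about half the time.

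*Non-completers dropped, missing = failure.* RT = *p*; SOC = *p*(1−*L*); gap = *pL*. At *L* = 0.05: 68.0 − 64.6 = 3.4 points.

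*Missing viral loads excluded.* Both groups are at *p*; gap 0.

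| Early loss per arm | Moved, missing = failure: gap (chance of p<0.05) | Dropped, missing = failure: gap (chance of p<0.05) | Missing excluded: gap |
|---|---|---|---|
| 2% | 2.7 (13%) | 1.4 (7%) | 0 |
| 5% | 6.5 (50%) | 3.4 (18%) | 0 |
| 10% | 12.4 (96%) | 6.8 (52%) | 0 |

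The ITT test stays at about 5% throughout. Variations on the moved, missing = failure case at 5%:
- 68% taken as the ITT rate, so *p* = 0.68/0.95 = 71.6%: 6.8 points.
- Only half of the 5% loss is early: 3.2 points.
- Everyone lost early is traced and 40% are suppressed: 2.7 points.

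**Reading 2: completion = blood drawn at Visit 1-RT.** No early loss changes group; gap 0.

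**Reading 3: completion = genotype result obtained.** Let *u* be the RT share without a result and *s* their Visit 3 suppression (assumed 50% to 90%), with 68% suppressed overall in each arm and non-completers moved. RT = (0.68−*us*)/(1−*u*); SOC = (0.68+*us*)/(1+*u*).
- *u* = 5%, *s* = 50%: 0.655/0.95 = 68.9% vs 0.705/1.05 = 67.1%, +1.8 points.
- *u* = 5%, *s* = 90%: 0.635/0.95 = 66.8% vs 0.725/1.05 = 69.0%, −2.2 points.
- *u* = 10%: +3.6 to −4.4 points.

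The shift is 0 if *s* = 68%.

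**The alternative estimator.** Take a true 10-point effect among those retained (68% vs 78%) and 5% early loss per arm.
- ITT difference: 0.95 × 10 = 9.5 points.
- As-treated (moved, missing = failure): 78.0 − 61.5 = 16.5 points.
- Complier-average: 9.5/0.95 = 10.0 if receipt means reviewed; 9.5/1 = 9.5 if it means obtained and every genotype succeeds.

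The definition moves the complier-average estimate by 0.5 point. With no true effect its numerator has expectation zero under either definition.

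**The case against.** A reader might infer that leaving completion undefined by itself builds 6.5 points into the analysis. The documents do not support that. The figure also needs reclassification, which the plan does not state; missing = failure, which is stated only for the ITT analysis; and a full 5% permanent early loss in each arm, which is an assumption. That censoring is listed as a separate sensitivity analysis makes keeping losses as failures plausible here, but no more than that.

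Table 2 also separates the resistance test at Visit 1-RT from the review at Visit 2-RT, so completing testing may more literally mean sample drawn or test performed. On either of those readings early losses do not move. Phone calls, home tracking and field blood draws (Sections V.E and VI.D) mean that missing the second visit need not mean missing the Visit 3 viral load, although home tracking was delayed during COVID-19. All of this stands, and it is why the result is a range.

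A reader might also infer that Visit 3 reflex tests would carry SOC failures into the RT group. The SOC clause relies on clinic records, whereas study tests come from the partner laboratories (Section VIII.A.5), and an analyst would probably exclude them. An explicit time limit would settle it.

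The strongest objection to the remedy is that a complier-average estimate assumes arm affects suppression only through the resistance result. RT participants without a result also lack the SOC repeat viral load, so this is only approximate. The error is small when non-completion is low: if 5% lacked a result and arm alone changed their suppression by an assumed 10 points, the estimate would shift by 0.05 × 10/0.95 = 0.5 point. The estimate also adds no power over the ITT test. Both limits should be stated; neither favours the as-treated version.

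**Conclusion.** The concern holds in a limited form. The as-treated analysis conditions on post-randomization events, and its bias depends on three rules the plan leaves open. With no true effect and an assumed 5% early loss per arm:
- about 6.5 points favouring RT if completion means reviewed, non-completers are moved and missing is failure;
- about 3.4 points favouring RT if non-completers are dropped and missing is failure;
- 0 if missing viral loads are excluded or completion means blood drawn.

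If completion means a genotype was obtained, the shift is roughly ±2 points at a 5% no-result rate, direction unknown. The loss rate, the no-result rate and the suppression of those without a result are assumptions.

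The primary ITT comparison is untouched, and the affected analysis is labelled secondary. This is a cheap improvement of minor priority.

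**What to change.** Before the arms are compared, amend Section X.B.4 as follows.

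1. Estimate the effect of receiving testing as a complier-average (instrumental-variable) effect with randomized arm as instrument: the ITT difference in suppression (missing = failure) divided by the between-arm difference in the share who received a resistance result before Visit 3, with a bootstrap interval.
2. Define receipt. In RT, the Visit 1-RT genotype was reviewed at Visit 2-RT; in SOC, a clinic-ordered test gave a result before Visit 3. Exclude Visit 3 reflex tests and later tests on stored plasma. Repeat with result obtained as the definition.
3. State the limit: RT participants without a result also lack the SOC repeat viral load, so the exclusion restriction is only approximate.
4. Keep any as-treated table as descriptive, labelled non-randomized, with the definition of completion, the grouping rule and the missing-data rule written down.
5. Report by arm how many had blood drawn, a result obtained and a result reviewed.

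The cost is about one paragraph, with no new visits or assays. Laboratory results and clinic records (Sections VIII.A.4 and VIII.A.5) supply result obtained and SOC receipt. Table 2 lists only a staff resource form at Visit 2-RT, so confirm that the date of result review is recorded there or can be derived from attendance.

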3. In both countries, For participants who cannot be reached by phone and/or if they do not attend clinic during the period of the COVID-19 pandemic, their study visits may fall outside of the Visit 3 timeline, and a study closure visit will be conducted as soon as possible once the COVID-19 pandemic subsides.

VIII. DATA COLLECTION AND MANAGEMENT

A. Sources of Data

1. Screening Form. Screening forms will be completed by research assistants prior to enrollment in order to confirm study eligibility.

2. Study questionnaires administered directly to study participants

- a. Sociodemographics Questionnaire at enrollment visit to collect basic age, sex, and socioeconomic data.
- b. EQ5D Quality of Life Questionnaire. EQ5D is a validated quality of life survey, that has been used both in populations with HIV infection and in sub-Saharan Africa [29-31]. This questionnaire will be administered at enrollment (Visit 1-SOC and Visit 1-RT) and again at Visit 3. The questionnaire will be instrumental in estimating cost-effectiveness of the intervention.
- c. Self-reported ART medication adherence. We will use a standardized ART medication adherence questionnaire, consisting of three questions about recent adherence. The questionnaire has been used and validated in sub-Saharan Africa, most notably in the Partners PREP study [28].
- d. Tracking form. A form will be completed that records participants name, clinic ID number, phone number(s), treatment supporter, and address information. This form along with the signed consent form will be retained in a locked file cabinet, but data from this form will not be entered into the study database, in an effort to optimize data confidentiality. The form will be used to locate missing study participants who do not present for follow-up study visits.

3. Resource Allocation Questionnaire collected from study clinician and study participant. At Visits 1 and 3, research assistants will complete data on resource allocation from the participant and study staff. This will include costs of medical care and clinic resources. This data will be used for the Budget Impact and Cost-Effectiveness Analyses.

4. Clinical records. Study staff will request clinical records of study participants. This will include participant charts and clinical, pharmacy, and/or clinical database data.

- a. HIV clinical history, including clinic enrollment date, ART start date, and ART regimen history

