1. Primary Outcome of Interest

Proportion of patients with a laboratory confirmed suppressed viral load, as defined by <200 copies/mL, at study conclusion (Visit 3).

2. Rationale for Primary Outcome of Interest

We have chosen this as our primary outcome to ensure a balanced outcome assessment 9 months after study initiation, standardization of viral load results across sites with different viral load testing platforms, and because it is an accepted international standard for other international studies of virologic suppression [39, 40].

3. Secondary Outcomes of Interest

- a. Proportion of patients with an undetectable viral load (below limit of detection) at study conclusion
- b. Proportion of patients with an undetectable viral load on first-line (NNRTI-based) therapy at study conclusion
- c. Proportion of patients with International AIDS Society-defined drug resistance mutations to their current regimen ^[41]. As part of this analysis, we will also evaluate for minority drug resistance.
- d. Total patient care costs, including diagnostic testing and ART costs for the study duration
- e. Retention in HIV clinical care at study completion
- f. 9-month mortality rate
- g. Change in health-related quality of life from baseline to 9 months

4. Efficacy Analysis Plan

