The goal of this analysis is to estimate total projected costs for treatment programs, comparing the WHO standard of care versus a resistance-testing based approach to management of virologic failure. We will follow International Society of Pharmacoeconomics Outcomes Research (ISPOR) guidelines to develop models to determine the budget impact of adopting resistance testing in South Africa and Uganda, respectively ^[42]. We will populate each model with data provided by the clinical trial on costs of care, and add country-specific HIV epidemiology, demographic and expenditure data to estimate the budget impact of adopting resistance testing over five years for each strategy. We will build the model such that country-specific fields will be flexible to enable analysis with other countries, to facilitate policy planning

and decision-making. Results of this analysis will advise HIV program partners on the net resources required in each country to implement routine resistance testing over a 5-year period.

2. Cost Effectiveness Analysis

If the resistance testing intervention is superior or similar to the standard of care strategy, we will proceed with a full cost-effectiveness analysis. This analysis seeks to build upon prior analyses that have considered the economics of resistance testing in sub-Saharan Africa [22-24]. We will achieve this by incorporating primary efficacy, quality of life, and cost data from the clinical trial, and by estimating the cost utility of resistance testing versus standard of care by selecting quality adjusted life years (QALY) as our primary outcome of interest.

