To do so, we will develop a cost utility model in accordance with best practice recommendations for modeling from the ISPOR Good Research Practice Task Force [43] and will follow the guidelines set out by the National Institute For Health and Clinical Excellence Reference Case [44]. We will develop a decision tree cohort Markov Model using TreeAge (TreeAge Software, Inc., Williamston, MA) with methods similar to those previously described by Rosen *et al* in their analysis of the cost effectiveness of resistance testing-based management of virologic failure [23]. The outcome of interest will be the cost per QALY (\$/QALY), presented as an incremental cost-effectiveness ratio. We will populate the model for the first 9 months with comparative efficacy, health-related quality of life (EQ5D questionnaire), and resource allocation data derived directly from the clinical trial. We will value health-related quality of life using the time trade off approach for a reference population in sub-Saharan Africa as adopted in similar HIV-related cost-effectiveness analyses [45]. Thereafter, we will use published data on the natural history of HIV disease to model clinical outcomes every 6 months after study conclusion over a patient's lifetime, including risk of opportunistic infections, hospitalization, quality of life and death [46-50].

We will vary the probability of each outcome by CD4 category, presence (or not) of detectable viral load and presence (or not) of resistance, to extrapolate cost utility (Table 7). To characterize uncertainty in the model, we will conduct a probabilistic sensitivity analysis (PSA), and present data as cost-effectiveness acceptability curves and PSA plots. Convergent validity will be undertaken to compare the model to similarly published models on the cost effectiveness of resistance testing. Whereas results will be immediately relevant for the South African and Ugandan populations, the proposed structure of the model will be designed such that it may be used for adaptation to countries with similar health care contexts. Results will be presented in US dollars to inform foreign stakeholders.

XI. HUMAN SUBJECTS CONSIDERATIONS

A. Study Risks and Discomforts

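### The efficacy plan tests quality of life only within participants, so secondary outcome (g) has no specified comparison between the arms

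*Combined protocol and SAP*

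**What the plan says.** Section X.B.3 lists the secondary outcomes; item (g) is "Change in health-related quality of life from baseline to 9 months". Section VIII.A.2.b names the instrument, EQ5D, and its timing: "This questionnaire will be administered at enrollment (Visit 1-SOC and Visit 1-RT) and again at Visit 3". Both arms therefore supply a baseline and a follow-up score.

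Section X.B.4 sets out the analyses in this order:

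- Primary outcome: "we will use a two-sample test of binomial proportions to compare the proportions of participants in each arm", and then "The unadjusted comparison of outcome rates will be followed by adjusted comparisons via logistic regression".
- Secondary endpoints: the primary analyses are followed by "similar statistical analyses of secondary endpoints including the proportions suppressed on first-line therapy, rates of resistance", with retention in care and mortality also named.
- Quality of life, in its own sentence: "We will compare health related quality of life measures within participants between baseline and study conclusion using paired t-tests". This sentence does not mention arm, and it does not say whether the tests are pooled or run separately by arm.

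Section X.C.2 makes a second use of the EQ5D data, under a condition: "If the resistance testing intervention is superior or similar to the standard of care strategy, we will proceed with a full cost-effectiveness analysis". If that analysis goes ahead, "We will populate the model for the first 9 months with comparative efficacy, health-related quality of life (EQ5D questionnaire), and resource allocation data" from the trial, and the result is an incremental cost per QALY.

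**The concern.** Aim 1 asks how resistance testing performs against viral-load-based management. An efficacy outcome should therefore be analysed by a contrast between the randomized arms. The test named for outcome (g) is a before-after contrast, so it gives no such estimate.

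In this trial a before-after change is to be expected whatever resistance testing does. Everyone enters with a viral load above 1,000 copies/mL, both arms receive adherence counselling, and both have a route to second-line therapy. The COVID-19 provisions (Sections VI.C and VII) also move some questionnaires to the telephone and let some final visits fall outside the Visit 3 window. All of this feeds directly into a paired test, whereas a randomized comparison would largely balance it.

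Two misreadings could follow. A significant pooled test could be taken as a benefit of the intervention. Separate tests by arm, one significant and one not, could be taken as a difference between the arms. If the analyst instead chose a between-arm method later, the choice would be made after data are in hand, for a self-reported outcome in an open-label trial.

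**Working it through.** The documents give no quality-of-life effect size, standard deviation or power, so there is no figure of the plan's own to reproduce. The check has three parts.

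**1. What each test addresses.** Let D(RT) and D(SOC) be the true mean changes in EQ5D from Visit 1 to Visit 3. Allocation is equal, about n = 420 per arm (Section X.A).

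- Pooled paired test: it concerns [n·D(RT) + n·D(SOC)] / 2n = [D(RT) + D(SOC)] / 2.
- Paired test by arm: it concerns D(RT) = 0 and D(SOC) = 0, separately.
- The randomized question: D(RT) − D(SOC).

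Neither of the first two is the third. Hypothetical values make this concrete:

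| Case | D(RT) | D(SOC) | Pooled mean change | Arm difference |
|---|---|---|---|---|
| A | 0.05 | 0.05 | 0.05 | 0 |
| B | 0.10 | 0.00 | 0.05 | 0.10 |

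The pooled mean change is the same in A and B, although the arms differ only in B.

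**2. Illustration of the misreading.** The assumptions are: change scores scaled to SD 1; the same true change c in both arms, so no arm effect; two-sided 5% tests; and 420 × 0.95 = 399 per arm. The 5% is the plan's invalid-test rate for viral load, borrowed here as an assumption. The chance that one arm's paired test is significant is about Φ(c√n − 1.96).

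- c = 0.2: Φ(0.2 × √399 − 1.96) = Φ(2.03) ≈ 0.98. In 4,000 simulated trials the one-arm paired test was significant in 98% and the pooled test in essentially all. A two-sample test of the change scores rejected in 4.4%.
- c = 0.1: Φ(0.1 × √399 − 1.96) = Φ(0.04) ≈ 0.515. The two arms' tests then disagree with probability 2 × 0.515 × 0.485 ≈ 0.50. The simulation gave 51%, against 4.9% rejections for the two-sample test.

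The values of c are invented for illustration and do not predict this trial.

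**3. Whether a between-arm analysis is feasible.** The smallest difference detectable by a two-sample comparison of change, in SD units of change, is (1.960 + z)·√(2/n), with z = 0.842 for 80% power and 1.282 for 90%.

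| n per arm | 80% power | 90% power |
|---|---|---|
| 399 | 0.20 | 0.23 |
| 420 | 0.19 | 0.22 |

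If EQ5D is nearly complete, the planned sample supports a useful comparison. The SD of change is not given, so this cannot be converted to EQ5D units.

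**The case against.** The best defence is that the list of secondary endpoints in X.B.4 is introduced as examples. Outcome (a), viral load below the limit of detection, is not named there either, yet it is plainly meant to be compared by arm. On this reading, similar analyses means an unadjusted and then an adjusted comparison by arm, with a method suited to the outcome, and the paired tests come in addition. This stands in part: absence from the list is weak evidence by itself. However, the methods referred back to are a test of proportions and logistic regression, which do not fit a quantitative score, and the next sentence gives quality of life a different test. Even on the generous reading, the plan names no between-arm method or estimate for outcome (g).

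A second defence is that Section X.C.2 compares the strategies using trial EQ5D data. It does, and the concern is therefore confined to the efficacy plan. But the model runs only if resistance testing is superior or similar, its output is cost per QALY, and it does not estimate or test the arm difference in outcome (g).

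Third, outcome (g) is the last of seven secondary outcomes, and the plan states no hypothesis or power for it. That is true, and it limits the weight of the point.

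**Conclusion.** The concern holds. Followed as written, Section X.B.4 specifies no randomized comparison for secondary outcome (g). This goes beyond missing detail, because the named test cannot answer the question of resistance testing against standard of care, whether it is pooled or run by arm.

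That conclusion rests on the identity above and on the wording of X.B.3 and X.B.4, and it needs no assumption about EQ5D. The simulated percentages and detectable differences depend on assumed effect sizes, normally distributed change scores with equal SD, and near-complete questionnaires; they serve only as illustration. The consequence is confined to one secondary outcome. The primary analysis and the sample size are unaffected.

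**What to change.** In Section X.B.4, make a between-arm comparison the analysis of outcome (g): a linear model of the Visit 3 EQ5D score on arm and baseline EQ5D score, with the stratification factors from Section IV.G (site, pregnancy, time since ART initiation) as covariates, reporting the mean difference and its 95% CI. A two-sample comparison of change scores would also meet the point; the adjusted model is the preferred form. Keep the paired changes by arm as descriptive results.

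The same edit should state which EQ5D score is analysed and how deaths and missing, telephone or out-of-window Visit 3 questionnaires are handled, since X.B.4 does not say so for this outcome.

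The cost is a few sentences, written before any EQ5D analysis by arm. EQ5D is already scheduled at Visits 1 and 3 in both arms, so no extra visits, participants or data collection are required.
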